## **14.4 12-Lead Electrocardiogram**

Electrocardiogram (ECG) data, such as clinical interpretation of ECGs, heart rate (HR) values, and interval assessments of RR, PR, QRS duration, QT interval, and the Fridericia's corrected value of the interval between the Q and T waves on the ECG tracing will be listed. Descriptive statistics for observed values and change from baseline will be summarized by cohort and scheduled time point for these 12-lead ECG interval and HR assessments.

The number and percentage of subjects meeting potentially clinically significant QTcF assessments ( $> 60$  increase from baseline;  $> 450$  msec in males;  $> 460$  msec in females) will be summarized by cohort.

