6.1.4. QT Stopping Criteria

Study drug will be discontinued for a participant if either of the following criteria is met:

- QTcF >500 msec OR uncorrected QT >600 msec
- Change from Screening in QTcF of >60 msec

One repeat ECG should be performed to confirm the accuracy and persistence of an initial result that fulfills the QT stopping criteria.

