#### *5.3.1.5 Electrocardiograms*

All 12-lead ECG assessments will include: heart rate, RR, PR, QRS, QT, and QTc intervals, preferably using Fridericia's formula. ECGs will be performed at Screening, Day 1 (pre-dose), Week 2, Week 12, and Safety Follow-up visits as shown in [Table 8](#) and [Table 10](#).

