#### 9.4.9 Baseline Values

Baseline values are defined as the last non-missing assessment that is on or prior to the date of the first dose of study drug in each cohort. If the date and time of an assessment are collected, then the date and time are compared against the first dose date and time; otherwise, if only the date of an assessment is collected, the baseline assessment will be the last non-missing assessment collected on or prior to the date of the first dose of study drug. A4, 17-OHP, and ACTH baseline values are defined as the mean of measurements collected between Screening (Visit 1) and Day 1 (Visit 2).

Subjects who re-enrolled into the same cohort, the last-non-missing assessment prior to the second enrollment's first dose of study drug will be used as baseline.

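### The QTcF table in SAP 14.4 has no count that matches the protocol's QT stopping criteria, so participants who met them can be found only by hand from listings

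*SAP*

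**What the plan says.** Protocol 6.1.4 (QT Stopping Criteria) discontinues study drug on an absolute criterion, "QTcF >500 msec OR uncorrected QT >600 msec", or on a relative one, "Change from Screening in QTcF of >60 msec". It adds a confirmation step: "One repeat ECG should be performed to confirm the accuracy and persistence of an initial result that fulfills the QT stopping criteria".

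SAP 14.4 (12-Lead Electrocardiogram) plans descriptive statistics and individual listings of the ECG intervals. It also plans one categorical table: "The number and percentage of subjects meeting potentially clinically significant QTcF assessments". Its categories are more than 60 "increase from baseline", above 450 msec in males and above 460 msec in females, all by cohort. The 60 carries no unit. The 450 and 460 limits are those of protocol exclusion criterion 7a, where a value above them leads to discussion with the Medical Monitor about eligibility.

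SAP 9.4.9 defines baseline as the "last non-missing assessment that is on or prior to the date of the first dose of study drug in each cohort". On ECG timing, SAP 5.3.1.5 states: "ECGs will be performed at Screening, Day 1 (pre-dose), Week 2, Week 12, and Safety Follow-up visits". Footnote 14 of the main-period schedules (protocol Appendices 1 and 3; SAP Tables 8 and 10) also refers to a pre-dose ECG on Day 1. The ECG rows of those same schedules mark Screening and leave Day 1 blank, and the Visit 2 activity list in protocol 3.1.2.2 contains no ECG.

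SAP section 15, which records departures from the protocol's analyses, does not mention the QTcF categories.

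**The concern.** A reader of the safety tables would expect to find how many participants reached the trial's own QT limits. The planned categories do not give that number. No row starts at 500 msec, no row covers uncorrected QT, and the row for a rise of more than 60 may use a different starting point from the stopping rule. The two absolute rows repeat entry-review limits that a participant may already exceed before the first dose. Because SAP 14.4 does not restrict them to new values, those rows can include people whose QTcF never moved.

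Safety is the primary objective, and protocol 1.3 names QTcF prolongation among the potential risks from the pre-clinical program (no cardiovascular concern had been noted in completed human studies). Under protocol 6.1.8, two participants in a cohort meeting individual stopping criteria lead to that cohort being stopped or dose-reduced. The number meeting 6.1.4 therefore bears on a design decision, yet no planned table reports it. SAP 14.2, by contrast, plans to identify and list participants who meet Hy's law criteria; QT has no counterpart.

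**Working it through.** The plan states no figure on this point to reproduce. The check sets the two sets of criteria side by side and runs illustrative ECG values through both. All QTcF values in the examples are assumptions, not trial data.

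**1. Criteria matched to rows**

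| Protocol 6.1.4 | Matching SAP 14.4 row |
|---|---|
| QTcF >500 msec | none; absorbed into >450 (males) or >460 (females) |
| Uncorrected QT >600 msec | none |
| QTcF rise >60 msec from Screening | rise >60 from baseline; the same only if baseline is the Screening ECG |

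**2. The absolute limit (does not depend on which ECG is baseline)**

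- Participant A: pre-dose 455, on treatment 505. Rise = 505 − 455 = 50. 505 > 500, so 6.1.4 is met. SAP 14.4 counts A only in the >450/>460 row.
- Participant B: pre-dose 440, on treatment 465. Rise = 465 − 440 = 25. No 6.1.4 criterion is met. SAP 14.4 counts B in the same row as A.

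**3. The relative limit (only if a Day 1 pre-dose ECG exists)**

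Values are Screening / Day 1 / Week 2 in msec.

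| Values | From Screening | From SAP baseline (Day 1) | 6.1.4 | SAP 14.4 |
|---|---|---|---|---|
| 380 / 395 / 445 | 445 − 380 = 65 | 445 − 395 = 50 | met | no row (445 is below 450 and 460) |
| 400 / 380 / 445 | 445 − 400 = 45 | 445 − 380 = 65 | not met | counted as >60 |
| 400 / 415 / 468 | 468 − 400 = 68 | 468 − 415 = 53 | met | not in the >60 row, but in the >450/>460 row |

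A participant who meets the Screening-based criterion escapes every SAP row only when two things hold together. First, the on-treatment QTcF is at most 450 (males) or 460 (females), so the Screening value lies below 450 − 60 = 390 or 460 − 60 = 400. Second, Day 1 exceeds Screening by at least the amount by which the rise passes 60. In the first example, Day 1 exceeds Screening by 395 − 380 = 15 and the rise passes 60 by 65 − 60 = 5.

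If Screening is the only pre-dose ECG, baseline equals Screening, the two rises are identical and this step falls away. Step 2 is unaffected.

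The documents give no within-person QTcF variability, so no frequency of disagreement can be derived. As an assumption only, a within-person SD of 8 to 12 msec gives a Screening-to-Day 1 difference with SD √2 × 8 = 11 to √2 × 12 = 17 msec. On that assumption a 15 msec gap would be unremarkable.

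**4. The uncorrected QT limit**

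Fridericia: QTcF = QT / RR^(1/3). QT = 600 with QTcF = 500 gives RR = (600/500)³ = 1.728 s, a heart rate of 60/1.728 = 34.7 bpm. At any faster rate, QT >600 already implies QTcF >500. A separate QT row would add little to a >500 row.

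**5. Grouping**

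SAP 14 says safety analyses are done by adult-equivalent dose level, while SAP 14.4 tabulates by cohort. Cohorts 5, 8 and 9 may each include both 300 and 400 mg BID, so a cohort row can mix doses. In a group of 5, one misplaced participant is 1/5 = 20%.

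**The case against.** The strongest reply is that a count table is not where individual cases are found. SAP 14.4 lists individual QT and QTcF values, SAP 11.1 lists discontinuations with their reasons, and SAP 14.1 has a separate listing of TEAEs leading to discontinuation. Protocol 7.2.1 makes an abnormal test result that leads to discontinuation reportable as an AE, so a QT stop should reach that listing. Groups are about 5 to 10, and the schedule for Cohorts 4 to 9 marks one routine on-treatment ECG, so reading the listing is little work. This stands. A reader might infer that the trial could not show who met the QT rule; the documents do not support that. What remains is that no flag for 6.1.4 is planned, and a participant who met a criterion without being stopped would have to be picked out from the ECG values.

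A reader might also infer that the two rules certainly measure the 60 msec rise from different ECGs. That is not established: the schedule rows and the Visit 2 list point to Screening as the only pre-dose ECG, against SAP 5.3.1.5 and footnote 14.

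Nor is this a breach of the protocol. Section 8.3.4.5 leaves the ECG categories open and does not ask that they mirror the stopping rule. Finally, 6.1.4 calls for a repeat ECG, so a table of single readings need not agree with discontinuations even after new rows are added. That is a fair point about the remedy, which should separate confirmed from unconfirmed readings.

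**Conclusion.** The point holds as a minor gap in a planned safety summary. As written, SAP 14.4 cannot give the number of participants who met the protocol's QT criteria, and it places values above 500 msec with values just over the entry-review limits. This part needs no assumption about which ECG is baseline.

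The second part is conditional. If a Day 1 pre-dose ECG is taken, a rise can be classed differently by protocol and SAP, in either direction, and in a narrow set of cases a participant who met 6.1.4 appears in no row. If it is not taken, the difference disappears. How often it would occur cannot be estimated from the documents.

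The primary endpoint (AEs and SAEs) and the real-time stopping rule are not affected. The consequence is a table that has to be supplemented by hand to answer an obvious safety question.

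**What to change.** In SAP 14.4:

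- Add post-dose counts for QTcF >500 msec and for meeting any 6.1.4 criterion, including the rise of more than 60 msec from Screening. State whether each case was confirmed on the repeat ECG. A separate row for uncorrected QT is optional, since the combined count covers it.
- Keep the rise of more than 60 from baseline as its own row and give its unit (msec).
- Show the >450 and >460 rows as new-onset, that is, among participants not above the limit before dosing.
- Present the table by adult-equivalent dose level, as SAP 14 requires.

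Separately, reconcile SAP 5.3.1.5 and schedule footnote 14 with the schedule ECG rows and the Visit 2 list, and state in the SAP which ECG serves as QTcF baseline. No change to the clinical stopping rule is proposed.

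The cost is a few table rows and one derived flag from ECG data already collected, plus a wording correction before database lock.

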## 14.5 Psychiatric Evaluations

The psychiatric evaluation assessments of suicidality, depression, and anxiety will be listed.

## 15 CHANGES RELATIVE TO THE PROTOCOL-SPECIFIED ANALYSIS

Study Protocol Section 8.2 defines the PD population as including “all subjects in the Safety Population with at least 1 evaluable post-baseline PD assessment.” Given the vague language in the protocol of how to determine eligibility for the PD population – if for example a subject must have a non-missing post-baseline from all six hormones (ACTH, 17-OHP, A4, testosterone, and 11KT), of any of the six PD hormones, or one specific hormone, the SAP added the specificity that the PD population includes “all subjects in the Safety Analysis Set with a baseline A4 assessment and at least one evaluable post-baseline PD A4 assessment” to align with the A4-dependent secondary efficacy analyses.

SAP [Section 8](#) additionally defines the Elevated Baseline Pharmacodynamic Analysis Set to support the secondary efficacy analysis of subjects with elevated baseline A4 who achieve a reduction in A4 at Week 4.

The Study Protocol Section 8.3.6 specifies that the hormone, 11-ketotestosterone (11-KT), will be summarized as part of the pharmacodynamic analyses, including: general summary statistics by visit, 11-KT/T ratio summaries by visit for males and females; and proportion of subjects with any reduction in 11-KT, a  $\geq 50\%$  reduction in 11-KT, and a normalization of 11-KT ( $11\text{-KT} \leq \text{ULN}$ ). 11-KT assessments, however, will not be provided to Spruce for this study. There are no standard assay or normal references of 11-KT for children. In addition, developing and validating an assay could not be completed in time for this study. Therefore, any protocol specified pharmacodynamic and exploratory endpoints for 11-KT will not be performed.

The Study Protocol Section 8.3.6 mentions that exploratory endpoint of the proportion of subjects with baseline dosing  $> 3 \times$  daily who decrease frequency of administration  $\leq 3 \times$  daily. Given that the dose frequency is collected in a free text form in the Concomitant Medication eCRF form, the dose frequencies are not standardized and easily analyzable, therefore GC medications will only be listed and not summarized to provide information supporting this exploratory endpoint.

The Study Protocol Section 8.3.4.1 states that “Using dosing data, estimates of exposure to tildacerfont will be summarized.” However, due to limitations in the collection of exposure and drug accountability data in this study, it is not possible to estimate tildacerfont exposure without making assumptions about the last dose date of the 12-week treatment period, the number of tablets dispensed, and the strength of the tablets dispensed. Therefore, information about exposure will only be listed on an individual basis as described in [Section 12.1](#).

## 17 APPENDIX A: SCHEDULE OF EVENTS

**Table 8** Schedule of Activities for Cohorts 1, 1a, 2, and 3

	Screening 	Treatment Period					Early Termination	Safety Follow-up 
		Day 1	Week 2	Week 4	Week 8	Week 12 (EOT)		
VISIT NUMBER	1	2	3	4	5	6		7
STUDY DAY	≤14 days before V2	1	14	28	56	84		Last dose +30 days
Visit windows			±3 days	±3 days	±3 days	±3 days		±7 days
Informed consent/assent	X							
Inclusion/exclusion criteria	X	X						
Demography & medical history	X							
Review of prior medications from past year	X							
Review of concomitant medications	X	X	X	X	X	X	X	X
Hepatitis B & C and HIV Screening	X							
Pregnancy test for FOCP 	X	X	X	X	X	X	X	X 
Laboratory assessments 	X	X	X	X	X	X	X	X 
Pharmacodynamics and Tildacerfont Concentration Samples (by Cohort)								
Cohorts 1 & 2 PD markers and tildacerfont concentration (serial, drawn together)  (also 1a if indicated)		X	X					
Cohorts 1 & 2 PD markers (single sample)  (also 1a if indicated)				X	X	X	X	X 
Cohorts 1 & 2 tildacerfont concentration (single sample)  (also 1a if indicated)				X	X	X	X	X 
Cohort 3 PD markers (single sample) 		X	X	X	X	X	X	X 
Cohort 3 tildacerfont concentration (single sample) 		X	X	X	X	X	X	X 
A4-based GC dose adjustment 				X	X	X		
Weight-based tildacerfont dose adjustment	X					X		
Urinalysis 	X		X			X	X	X 

	Screening 	Treatment Period					Early Termination	Safety Follow-up 
		Day 1	Week 2	Week 4	Week 8	Week 12 (EOT)		
VISIT NUMBER	1	2	3	4	5	6		7
STUDY DAY	≤14 days before V2	1	14	28	56	84		Last dose +30 days
Visit windows			±3 days	±3 days	±3 days	±3 days		±7 days
Vital signs  , body weight	X	X	X	X	X	X	X	X 
Physical exam 	X	X	X	X	X	X	X	X 
12-lead ECG	X		X 			X	X	X 
Bone age and predicted adult height 	X							
C-SSRS 	X		X	X	X	X	X	X 
PROMIS 	X		X	X	X	X	X	X 
SWYC 	X		X	X	X	X	X	X 
Dispense study drug 		X						
Study drug accountability			X	X	X	X	X	
Clinic drug administration 		X	X					
Review any AEs		X	X	X	X	X	X	X

Abbreviations: 11KT=11-ketotestosterone; A4=androstenedione; ACTH=adrenocorticotropin hormone; AEs=adverse events; ALT=alanine aminotransferase; ALP=alkaline phosphatase; AST=aspartate aminotransferase; CRO=contract research organization; C-SSRS= Columbia-Suicide Severity Rating Scale; ECG=electrocardiogram; eGFR=estimated glomerular filtration rate; EOT=end of treatment; ET=early termination; FOCP=female of childbearing potential; GC=glucocorticoid; GGT=gamma-glutamyl transferase; HIV=human immunodeficiency virus; EP=open-label extension; PD=pharmacodynamics; PK=pharmacokinetics; PROMIS=Patient Reported Outcomes Measurement Information System; 17-OHP=17-hydroxyprogesterone; SWYC=Survey of Well-being of Young Children; T=testosterone.

 The Screening Period may be extended as approved by the Sponsor or CRO designee.

 For participants continuing in the EP period, the Safety Follow-up Visit will be 30 days after their last dose in the EP Period.

 A pregnancy test will be performed at every visit for FOCP. The Screening Visit will include a serum pregnancy test. All subsequent visits will include urine pregnancy tests. Any positive urine pregnancy test must be followed up by a serum pregnancy test for confirmation.

 Labs will be drawn at approximately 8 AM (±1 h) before any morning dose of GC medication.

 Laboratory assessments include: coagulation panel (Screening only), hematology, chemistry (including liver function tests AST, ALT, ALP, GGT, total and direct bilirubin, and total bile acids), thyroid panel. Fasting is not required.

 As needed based upon safety concerns, per Investigator discretion.

 For Cohorts 1 and 2, serial blood samples at 3 timepoints to assess PD (ACTH, 17-OHP, A4, testosterone and 11KT) cortisol and tildacerfont concentrations: pre-dose (prior to GC dosing and tildacerfont dosing), 0.5 to 1.5 hours post GC and tildacerfont dose, and 3 to 5 hours post-GC and tildacerfont dose.

 PD Samples (ACTH, 17-OHP, A4, testosterone, 11KT). They must be drawn prior to GC dosing, at approximately 8 AM (± 1 h). Fasting is not required.

 Tildacerfont concentration collected prior to GC dosing. Fasting is not required.

 In all cohorts, GC dose (frequency or total daily dose) may be adjusted based on A4 levels collected at Weeks 4 and 8 (all participants) and Week 12 (for those participants continuing in the optional EP). If a change in GC is warranted by the A4 algorithm, sites will contact participants by telephone after receipt of results (within approximately 2 weeks) after each applicable study visit.

 Urinalysis should include the following: specific gravity, pH, glucose, protein, blood, ketones, bilirubin, urobilinogen, nitrite, by dipstick. Microscopic examination should be obtained if blood or protein is abnormal. For visits in which tildacerfont is administered, urinalysis should be performed pre-dose.

 Systolic and diastolic blood pressure, pulse rate, body temperature, and respiration rate. Height will only be collected every 6 months.

 Full physical exam is performed at Visit 2, Visit 6, and ET Visit; an abbreviated/directed physical exam is performed at all other visits.

 Day 1 ECGs are conducted pre-dose. Day 14 ECG is dose independent, as participants should be at steady state.

 Historical bone age and predicted adult height calculation may be used if performed  $\leq$ 6 months prior to Screening. If no appropriate image is available, x-ray of left hand and wrist will be performed to assess bone age and calculate predicted adult height.

 The C-SSRS, to assess suicidality, is only conducted for participants aged 6 to 17 years.

 PROMIS, to assess anxiety and depression, is conducted for participants aged 5 to 17 years.

 The SWYC to assess anxiety and depression is only conducted in Cohort 3 participants  $\leq$ 5 years of age.

 A 12-week supply of study drug will be dispensed at Visit 2 (Day 1). Participants should bring study drug to all visits for accountability. Upon receipt of study drug, the pharmacy will hold/store two doses to ensure that in-clinic dosing can occur at Visit 3 (Week 2) in the event a participant does not bring study drug to the visit.

 Cohorts 1 and 2 dosing:

Cohorts 1 and 2 (and 1a if indicated) will dose with a morning meal for the first 14 days of the study. Cohorts 1 and 2 (and 1a if indicated) will take the study drug at the clinic on Day 1 (Visit 2) (to allow for a 1-hour safety observational period and serial tildacerfont concentrations), and on Day 14 (to allow for serial tildacerfont concentrations).

Starting on Day 15, Cohorts 1 and 2 will switch to taking the study drug with their evening meal for the duration of the study.

Cohort 3 dosing:

Cohort 3 will dose with a morning meal at the study clinic on Day 1 (Visit 2) to allow for a 1-hour observational period. All subsequent doses for Cohort 3 will occur with evening meals.

**Table 9 Schedule of Activities for Open-label Extension for Cohorts 1, 1a, 2, and 3**

	Week 12	Week 24	Week 36	Week 48	Week 60	Week 72	Week 84	Week 96 (EOT)	Early Termination	Safety Follow-up (Phone call)
VISIT NUMBER	6	7	8	9	10	11	12	13		
Visit windows	±2 weeks		Last dose +30 days							
Informed consent/assent	X									
Concomitant medications	X	X	X	X	X	X	X	X	X	X
Pregnancy test for FOCP 	X	X	X	X	X	X	X	X	X	
Laboratory assessments 	X	X	X	X	X	X	X	X	X	X 
PD and tildacerfont samples 	X	X	X	X	X	X	X	X	X	X 
A4-based GC dose adjustment 	X	X	X	X	X	X	X			
Weight-based tildacerfont dose adjustment	X	X	X	X	X	X	X			
Urinalysis 				X		X		X	X	X 
Vital signs  , body weight	X	X	X	X	X	X	X	X	X	X 
Abbreviated/directed physical exam	X	X	X	X	X	X	X	X	X	X 
C-SSRS 	X	X	X	X	X	X	X	X	X	X 
PROMIS 	X	X	X	X	X	X	X	X	X	X 
SWYC 	X	X	X	X	X	X	X	X	X	
Bone age and predicted adult height 		X		X		X		X		
Dispense study drug	X	X	X	X	X	X	X			
Review any AEs	X	X	X	X	X	X	X	X	X	X
Study drug accountability	X	X	X	X	X	X	X	X	X	

Abbreviations: 11KT=11-ketotestosterone; A4=androstenedione; ACTH=adrenocorticotropin hormone; AEs=adverse events; ALT=alanine aminotransferase; ALP=alkaline phosphatase; AST=aspartate aminotransferase; C-SSRS=Columbia–Suicide Severity Rating Scale; ECG=electrocardiogram; EOT=end of treatment; ET=early termination; FOCP=female of childbearing potential; GC=glucocorticoid; GGT=gamma-glutamyl transferase; PD=pharmacodynamics; PROMIS= Patient Reported Outcomes Measurement Information System; 17-OHP=17-hydroxyprogesterone; SWYC=Survey of Well-being of Young Children; T=testosterone.

 A serum pregnancy test will be performed at Screening for FOCP only. All subsequent tests will be urine pregnancy tests

 Labs will be drawn at 8 AM (±1 h) before any morning dose of GC medication.

 Laboratory assessments include: hematology, chemistry (including liver function tests AST, ALT, ALP, GGT, total and direct bilirubin, and total bile acids), thyroid panel. Fasting is not required.

 As needed based upon any safety concerns, per Investigator discretion.

 PD Samples (ACTH, 17-OHP, A4, testosterone, and 11KT). They must be drawn prior to GC dosing. Fasting is not required. Single samples for plasma concentration of tildacerfont will be drawn at all visits.

 GC dose (frequency or total daily dose) may be adjusted based on A4 levels collected at each visit. If a change in GC is warranted by the A4 algorithm, sites will contact participants by telephone after receipt of results (within approximately 2 weeks) after each applicable study visit.

 Urinalysis should include the following: specific gravity, pH, glucose, protein, blood, ketones, bilirubin, urobilinogen, nitrite, by dipstick. Microscopic examination should be obtained if blood or protein is abnormal.

 Systolic and diastolic blood pressure, pulse rate, body temperature, and respiration rate.

 The C-SSRS, to assess suicidality, is only conducted for participants aged 6 to 17 years.

 PROMIS, to assess anxiety and depression, is conducted for participants aged 5 to 17 years.

 The SWYC to assess anxiety and depression is only conducted in Cohort 3 participants under 5 years of age.

 Historical bone age and predicted adult height calculation will be performed by an x-ray of left hand and wrist to assess bone age and calculate predicted adult height

